#### Inferential statistics

The primary outcome of the trial understands of research results presented in various summary formats by lay persons. Each question has a single possible answer and the participant's result is the sum of the correct answers. Also, it is possible to determine how each one of the demographic characteristics predicts correct answer on the knowledge test using logistic regression.

For overall reading experience and accessibility of information between group testing we plan to test the distributions of the variables, and then to choose the non-parametric test (Kruskall-Wallis test) if the distribution of results is not normal or to choose the parametric test (ANOVA) if the distribution of results is normal.

Table 1 Overview of the outcome measures

Outcome	Scale	Measure	Methods of analysis
Understanding	Dichotomous	Sum of correct answers	Kruskall-Wallis/ANOVA
Accessibility of information	Continuous	Likert-type scale from 1 to 10	Kruskall-Wallis/ANOVA
Reading experience	Continuous	Likert-type scale from 1 to 10	Kruskall-Wallis/ANOVA
Health numeracy	Dichotomous	Sum of correct answers	Kruskall-Wallis/ANOVA; Spearman correlation coefficient with understanding outcome

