#### Claiming of the non-inferiority

For the primary outcome, non-inferiority of the experiment format to the control formats will be claimed if the lower limit of the CI (for the difference in average results between intervention group and control groups) is higher than the non-inferiority margin of 20%. The tests of superiority will be applied to the secondary outcomes. We want to perform the non-inferiority testing in order to prove that infographic is no worse than PLS and scientific summaries for information translation in terms of understanding of information. Also, the superiority tests will show that the infographic is better in terms of user satisfaction and accessibility of information compared to standard PLS and scientific summaries.

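### The non-inferiority rule needs a confidence interval for a difference in mean score, but the tests listed for the primary outcome are three-group omnibus tests that do not give one

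*Combined protocol and SAP*

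**What the plan says.** Under *Claiming of the non-inferiority*, the plan declares the infographic non-inferior on the primary outcome from "the lower limit of the CI (for the difference in average results between intervention group and control groups"), judged against a 20% margin. Secondary outcomes are to be tested for superiority. The section does not say how the interval is calculated, at what confidence level, or how the comparisons with the two control formats combine into one claim.

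Under *Inferential statistics*, the Table 1 row for the primary outcome reads "Understanding Dichotomous Sum of correct answers Kruskall-Wallis/ANOVA". The row carries no rule for choosing between the two tests. The *Outcomes* section defines the variable as a score from 0 to 10.

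A selection rule appears only in the text above the table, and its scope is stated: "For overall reading experience and accessibility of information between group testing we plan to test the distributions of the variables". Within that scope the rule is "we plan to test the distributions of the variables, and then to choose the non-parametric test" (Kruskal-Wallis) if the distribution is not normal, or "to choose the parametric test (ANOVA) if the distribution of results is normal". The distribution test, its level, and whether it is applied per group or to residuals are not given.

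The *Sample size* section sets a minimum of 15 completers per group and gives no SD.

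**The concern.** The decision rule and the listed analysis answer different questions. The rule asks how far the infographic mean could lie below one control mean. The listed tests ask whether any of three groups differs from the others, on means or on ranks. A p-value from either cannot be compared with a margin. At the analysis stage someone will have to choose an interval method, a level and the pairwise contrasts after seeing the data, and with small groups those choices can decide a borderline claim.

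A second, smaller issue follows. If the pre-test is carried over to the knowledge score, the data also decide whether the trial compares means or ranks. That choice can differ from one outcome to the next.

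**Working it through.** **1. Set the rule beside the listed analyses**

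- Rule: lower limit for a pairwise mean difference, infographic minus a control format.
- Kruskal-Wallis: one p-value across three groups, based on ranks. It gives no interval for a difference in means.
- One-way ANOVA: one F test across three groups. It gives no pairwise interval until contrasts are named, and none are.

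The gap is therefore present whichever test is chosen.

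**2. The planning figure used as an input**

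The plan's 15 per group comes from alpha 0.05, 80% power and a 40-point difference. The two-sided pooled formula is n = [1.96√(2p̄q̄) + 0.8416√(p₁q₁ + p₂q₂)]² / (p₁ − p₂)².

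- 80% v 40%: (1.358 + 0.532)² / 0.16 = 22.3, so 23.
- 80% v 30%: (1.379 + 0.512)² / 0.25 = 14.3, so 15.

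The stated 40-point contrast does not reproduce 15. That is a separate matter, and 15 is taken as given here.

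**3. What the missing interval would look like**

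Assumptions: the 20% margin is read as −2 points on the 10-point scale; SDs of 1.5 to 3 are assumed.

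- 95% half-width = t(0.975, 28 df) × SD × √(2/15) = 2.048 × 0.365 × SD = 0.748 × SD.
- Chance of meeting the margin for one comparison when the true difference is 0 = Φ(2 / (SD√(2/15)) − 1.96).

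| Assumed SD | 95% half-width (points) | Chance of meeting the margin |
|---|---|---|
| 1.5 | 1.12 | 95% |
| 2 | 1.50 | 78% |
| 2.5 | 1.87 | 59% |
| 3 | 2.24 | 45% |

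With equal groups, either omnibus test is non-significant in about 95% of trials. The interval meets the margin in anything from 95% down to 45%. The omnibus result therefore does not settle the non-inferiority question.

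The unstated level matters too. At SD 2 the standard error is 2 × 0.365 = 0.730. With an observed difference of −0.6, the 95% lower limit is −0.6 − 1.50 = −2.10, which misses −2. The 90% limit is −0.6 − 1.701 × 0.730 = −1.84, which meets it.

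**4. How the pre-test would behave if applied to the knowledge score**

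Three equal groups of 15 were simulated, with Shapiro-Wilk at 0.05 followed by Kruskal-Wallis or ANOVA. Two assumed score models were used: normal scores rounded and clipped to 0-10 (3,000 trials per setting), and beta-binomial scores out of 10 (2,000 per setting). For the beta-binomial, SD = √[10m(1 − m)(1 + 9ρ)], where m is the mean proportion correct; for example, m = 0.8 and ρ = 0.15 give √(1.6 × 2.35) = 1.94. The first mean-5 row uses ρ = 0.01 and the other beta-binomial rows use 0.15.

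| Score model | Mean | SD | Kruskal-Wallis chosen: residual pre-test | Kruskal-Wallis chosen: any group rejects |
|---|---|---|---|---|
| Rounded normal | 6 | 1.5 | not run | 53% |
| Rounded normal | 6 | 2 | not run | 30% |
| Rounded normal | 8 | 1.5 | not run | 68% |
| Rounded normal | 8 | 2 | not run | 80% |
| Beta-binomial | 5 | 1.65 | 13.5% | 43.2% |
| Beta-binomial | 5 | 2.42 | 10.4% | 23.6% |
| Beta-binomial | 6 | 2.37 | 21.9% | 30.7% |
| Beta-binomial | 8 | 1.94 | 93.2% | 96.6% |

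Type I error of the two-stage procedure was 4.2% to 5.8% for the beta-binomial scores and about 5% for the rounded normal scores. ANOVA and Kruskal-Wallis disagreed on significance in 0.6% to 2.5% of trials and in 1.5% to 5%, respectively.

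**The case against.** Four points on the other side carry weight.

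- **The pre-test sentence does not cover the primary outcome.** This stands. It names two secondary outcomes, which are tested for superiority and need no non-inferiority interval. A reader might infer that the plan applies the pre-test to the knowledge score because Table 1 lists the same pair of tests. The documents do not say so. The point has to rest on the Table 1 row for Understanding and the non-inferiority section.
- **An interval for a mean difference can be calculated whichever test is run.** This stands too. The non-inferiority section sits under its own heading, and the omnibus tests suit the equality hypothesis in the *Objectives* section. Table 1 may have been written for that hypothesis. But then the plan names no analysis at all for the interval on which its primary claim rests.
- **The ANOVA branch is not adequate either.** A reader might infer that the interval is lost only when normality is rejected. That is not so: the F test lacks it as well, and dropping the pre-test alone would not supply it.
- **Kruskal-Wallis is not shown to be the likelier branch.** The high figures need all groups to average about 8. The 80% in the *Sample size* section is a proportion of participants answering correctly with one format in cited studies, set against 20-40% without it; it is not a mean score for every group. The any-group rule would also reject in 1 − 0.95³ = 14% of trials with perfectly normal data.

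For the secondary scores, the practical harm shown is small. Means and SDs are already to be reported under *Descriptive statistics*.

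**Conclusion.** The point holds for the primary outcome. The non-inferiority decision depends on an interval for a pairwise mean difference, and neither analysis listed for Understanding produces it. The interval's method and level and the contrasts are all unspecified. At 15 per group the 95% half-width is about 1.1 to 2.2 points for assumed SDs of 1.5 to 3, against a margin of 2 points, so these choices can decide the claim.

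The pre-test is a secondary matter. If it is extended to the knowledge score, the chosen test varies with chance and ceiling effects, from roughly 10% to 97% Kruskal-Wallis under the assumptions tried. A reader might infer an inflated false-positive rate; the simulations do not support that (about 4-6%). What is lost is a fixed effect measure and a primary rule with a matching analysis.

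The conclusion about the missing interval needs no distributional assumption. The sizes rest on assumed SDs and score distributions, and on reading the margin as 2 of 10 points. This is a cheap improvement.

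**What to change.** For Understanding, replace the Table 1 entry with two pre-specified differences in mean score, infographic minus PLS and infographic minus scientific summary. Give each a confidence interval at a stated level. Choose one interval method now (linear-model contrasts, Welch or bootstrap), so that it is not picked from the data. Name this as the analysis for the non-inferiority rule, and say whether the claim requires both comparisons to meet the margin. Keep Kruskal-Wallis as a sensitivity analysis.

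As a minor addition, drop the distribution pre-test for reading experience and accessibility and use the same mean-difference analysis there.

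The cost is SAP wording; no stated sample size changes. The downside is slightly lower efficiency than a rank test if the scores are heavily skewed.

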### Data Management

Since the trial will be performed during the first lecture of a mandatory graduate course, we do not expect significant dropout. If a participant decides to leave during the trial, his or her results will not be included in the analysis. The participants will be not able to learn about their results after the trial as the identity of the participants will be unknown to the researchers. We will try to reduce the possibility of missing data in a way that the testing interface will not allow the respondent to move to the next page until all questions on the current page are answered. As the primary outcome is knowledge examination, the order of the questions will be the same for all the participants so that we could avoid interference of other contents, which could have an adverse impact to the results.

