### Trial design

We will conduct a randomized control trial (RCT) with three different formats of the same systematic review summary (infographics, PLS and scientific summary). The content of these three formats is based on the same systematic review, but the ways of data presentation will differ: visual presentation in plain language, plain language, and scientific language. The trial will be performed at the beginning of the 2016/2017 academic year, with physicians as participants. The trial will be voluntary and anonymous. The survey will consist of 4 parts: 1) demographic data, 2) one format of the summary (randomly assigned), 3) comprehension test

of the information given in the summary, 4) accessibility of information and overall satisfaction with the given summary assessed by survey and 5) health numeracy test. All materials will be in Croatian. The materials used in this research will be assessed by experts in order to confirm face validity of the survey.

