## **Methods: Participants, interventions, and outcomes**

### Setting and recruitment

The trial will be performed online using SurveyMonkey software (A/B testing method).

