### Eligibility criteria

Eligible participants will be medical doctors in any specialty or field of work. Authors will make a list of publicly available e-mail addresses of doctors—clinical researchers from the School of Medicine and University Hospital Center in Split to make an email list of potential participants

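### Read literally, the rule on participants who leave removes completed primary knowledge scores when someone quits during the 16 items that follow the test

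*Combined protocol and SAP*

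**What the plan says.** All references are to the combined protocol and SAP.

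- **Exclusion rule (Data Management):** "If a participant decides to leave during the trial, his or her results will not be included in the analysis". It makes no exception by outcome or by the point at which the person leaves. No other section defines an analysis set, keeps partial responders or plans a sensitivity analysis.
- **Order of the survey (Trial design):** the comprehension test is third, accessibility and satisfaction fourth, and last comes "5) health numeracy test". The section announces four parts and then lists five, but the order is clear.
- **Fixed order and page gating (Data Management):** "the order of the questions will be the same for all the participants", and the interface blocks progress until the current page is complete.
- **Expected dropout (Data Management):** "Since the trial will be performed during the first lecture of a mandatory graduate course, we do not expect significant dropout". No rate is given.
- **Anonymity:** "The trial will be voluntary and anonymous" (Trial design), and "the identity of the participants will be unknown to the researchers" (Data Management).
- **Sample size:** at least 15 people per group, counted as people who complete the survey.

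**The concern.** A participant who stops in the satisfaction or numeracy items has already supplied everything the primary analysis needs. Dropping that score because secondary items are unfinished loses primary data, and the documents give no reason for it.

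Leaving also happens after the format has been seen, so membership of the primary analysis depends on behaviour after randomisation. If leaving differs by format and is related to score, the comparison is biased. Recruiting until 15 per group have completed would protect precision but would not undo that selection. Because the plan does not ask for leaving to be reported by arm, a reader of the results could not judge whether it mattered.

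**Working it through.** **Step 1: the plan's own figures.** There is no dropout figure to reproduce. The only related number is 15 completers per group. It is obtained for 80% against 30%, two-sided 5%, 80% power, pooled variance: [1.96·√(2·0.55·0.45) + 0.84·√(0.8·0.2 + 0.3·0.7)]² / 0.5² = 14.3, rounded up to 15. The plan does not state that variant. The point here does not depend on it.

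**Step 2: who is affected.** The knowledge test has 10 questions (Outcomes). After it come reading experience (5, Outcomes and Survey C1), accessibility (5, Survey C2) and numeracy (6, Survey C3): 5 + 5 + 6 = 16 of the 26 items that follow the summary. The first item of Survey C2 asks about answering the test, which confirms that it comes later. With page gating, anyone who has reached the later parts has answered all ten knowledge questions. This assumes that the test does not share a page with later items, since the page layout is not given. The rule costs data only for these late leavers. Those who leave before submitting the test have no complete score to keep.

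**Step 3: an illustration.** All inputs are assumed. Take two arms A and B with the same true mean of 6 out of 10. Leaving is 10% in A and 30% in B, half before and half after the test, and leavers score 2 points below stayers.

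- Stayers' mean = 6 + (proportion leaving × gap): A 6 + 0.10·2 = 6.20; B 6 + 0.30·2 = 6.60. Under the current rule, B − A = **+0.40**.
- Keeping submitted tests: A (0.90·6.2 + 0.05·4.2)/0.95 = 6.095; B (0.70·6.6 + 0.15·4.6)/0.85 = 6.247. B − A = **+0.15**.
- Part due to the rule: 0.40 − 0.15 = **0.25**. The remaining 0.15 comes from early leavers and would be there under either rule.

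**Step 4: does keeping the scores always help?** Same leaving rates, other assumed gaps relative to stayers:

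| Early leavers | Late leavers | Current rule | Tests kept |
|---|---|---|---|
| 2 lower | 2 lower | +0.40 | +0.15 |
| 4 lower | same | +0.40 | +0.40 |
| same | 4 lower | +0.40 | −0.10 |
| 2 lower | 2 higher | 0.00 | +0.25 |

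In the last row the stayers' mean is 6.00 in both arms, because the two gaps cancel. With tests kept, A is (0.90·6 + 0.05·8)/0.95 = 6.105 and B is (0.70·6 + 0.15·8)/0.85 = 6.353. Here retention increases the bias.

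**Step 5: what retention does secure.** The unknown scores fall from 10% and 30% of the two arms to 5% and 15%. If each unknown score could lie anywhere from 0 to 10, the width of the worst-case range for B − A falls from 10·(0.10 + 0.30) = 4.0 points to 10·(0.05 + 0.15) = 2.0 points. With the Step 3 means, that is −1.96 to +2.04 against −0.98 to +1.02.

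**Step 6: scale.** At an assumed SD of 2 and 15 per arm, the standard error of a difference is 2·√(2/15) = 0.73, so 0.25 is about a third of one standard error. If the 20% non-inferiority margin is read as a share of the 10-point scale (2 points), 0.25 is one eighth of it.

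**The case against.** The strongest reply is that leaving may have been meant as withdrawing consent, in which case exclusion is proper. That is a possible reading. The sentence does not separate the two, so what is firm is a rule that drops completed scores when taken literally.

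The second reply is that the effect is unquantified. That stands. The documents give no leaving rate, no score gap and no SD, and they do not show that leaving would differ by format or be related to score.

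The third is that the replacement still conditions on behaviour after randomisation, because it requires a submitted test, and that it can do worse, as the last row of the table shows. Both stand. The case for it is that it uses every primary score collected and leaves fewer unknown, and bias reduction cannot be promised.

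Two stronger readings are tempting and should be resisted:

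- A reader might charge the whole false difference among completers to this rule. That would count early leavers, whom the rule does not affect. Only the late-leaver share belongs to it.
- A reader might infer that a voluntary, anonymous online survey in itself contradicts a mandatory lecture. It does not: a voluntary online questionnaire can be run in a lecture, and Data Management itself describes a gated testing interface. The real conflict is over population and recruitment. Trial design and Eligibility criteria describe physicians ("Eligible participants will be medical doctors in any specialty or field of work") on an e-mail list, while Participant timeline, Sequence generation and Data Management describe students on a course.

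**Conclusion.** The concern holds as a defect of wording in who enters the primary analysis. As written, the rule discards complete primary scores from anyone who quits during the 16 later items, and no other section rescues them. This is so whether the participants are physicians or students.

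Its size cannot be derived from the documents. Under the assumed inputs of Step 3 the rule accounts for 0.25 of a 0.40-point false difference on a 10-point scale, which is small against the sampling error at 15 per arm. Other assumptions change its size or sign. The documents do not support a claim that the trial's result would be biased in a given direction, nor that retention would remove bias.

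It is worth correcting because the change is cheap and because, in an anonymous survey, partial responses not stored with the assigned format could not be recovered later. The expectation of little dropout cannot be relied on until the population is settled, because it rests on the course setting.

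**What to change.** Replace the exclusion sentence in Data Management with:

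> The primary analysis includes every randomised participant who submitted the knowledge test, in the assigned group, whether or not parts 4-5 were completed, unless the participant asked within the survey for the data to be withdrawn.

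Then:

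- Provide a way to record a withdrawal request inside the survey, since responses are anonymous.
- Store partial responses with the assigned format.
- Report, for all three arms, the number shown each format and the number completing each part.
- If a worst-case bound for early leavers is added, define it separately for infographic against PLS and for infographic against scientific summary, and present it as a bound, not a correction.
- Separately, reconcile the population and recruitment across Trial design, Eligibility criteria, Participant timeline, Sequence generation and Data Management, and restate the dropout expectation to match. Correct the count of survey parts in Trial design at the same time.

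The cost is slightly different numbers analysed for the primary and secondary outcomes, one table of counts, and a check before launch that the survey set-up keeps partial responses, which the documents do not state.

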### **Ethics and dissemination**

The approval of the Ethical Committee of University of Split School of Medicine has been obtained under the ethics approval for the grant “Professionalism and Health” funded by the Croatian Science Foundation (Grant No. IP-2014-09-7672).

